### **6.3. Other Endpoint(s)**

#### **6.3.1. Analysis of PK Endpoints**

Plasma tofacitinib concentration data will be listed by individual subject and time point. Oral clearance (CL/F) and other pharmacokinetic (PK) parameters calculated from plasma tofacitinib concentrations are out of scope of this SAP and will be reported separately.

#### **6.3.2. Analysis of Exploratory Endpoints**

Exploratory or pooled analyses, if conducted utilizing the biobanked genomic and/or biomarker samples from this study, will be documented in a separate analysis plan.

## 6.4. Subset Analyses

No subgroup analyses will be done for OL endpoints. The primary endpoint (time to flare in the DB phase) and some secondary endpoints (occurrence of disease flare, achieving ACR 30/50/70 and JIA ACR inactive disease at each scheduled visit in double-blind phase) will be summarized by age group at enrollment, baseline body weight, geographical region, formulation, and treatment history (OL Day 1 oral corticosteroid use, OL Day 1 MTX use, and prior bDMARD experience) by treatment and visit. Details are as follows.

### Age Group Analyses

Subgroup analyses will be presented for age group at enrollment: from 2 to  $<6$  years, from 6  $<12$  years, and from 12 to  $<18$  years.

The primary endpoint of time to flare in the DB phase will be analyzed by these subgroups. The same methodology and summary as the primary analysis in [Section 6.1.1](#) will be done (Estimand 1). I.e, K-M estimates of median time to flare and quartiles, as well as probabilities of not having flare up to all the DB monthly visits will be generated for the tofacitinib and placebo treatment groups by age subgroup. Hazard ratios (toccitinib/placebo) and corresponding 95% confidence intervals may be provided for the time-to-flare analysis. The secondary endpoints of ACR 30/50/70 response and JIA ACR inactive disease by visit in the DB phase will be analyzed similarly as in [Section 6.2.1.1](#) by age subgroup (Estimand 2).

Subgroup analyses similar to the above age group analyses (Estimand 1 and Estimand 2) will also be presented for:

- Baseline body weight:  $<40$  kg and  $\geq 40$  kg
- Geographic region: North America [US and Canada], South and Central America [Brazil, Argentina, Mexico, Costa Rica], Europe [Poland, Belgium, Great Britain, Spain, Hungary, Germany, and Italy], Asia [China, India], and Rest of World [Ukraine, Turkey, Russia, Australia, Israel, and South Africa]

- Formulation: tablet and solution

Note: subjects who take both formulations will be excluded

- OL Baseline (Day 1) oral corticosteroid use: Yes and No
- DB Baseline (Randomization Day) oral corticosteroid use: Yes and No
- OL Baseline (Day 1) MTX use: Yes and No
- Prior bDMARD experience (any time on or before OL Day 1): Yes and No

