3.2.1. Open-label Phase, Part 1: Treatment with Tofacitinib while on Stable Background Therapy

Part 1 of the open-label active treatment phase is designed to identify tofacitinib-treated subjects who are able to achieve and maintain an Adapted JIA ACR 30 response for at least 4 weeks while continuing on the stable CS dose identified during the screening period prior to treatment with tofacitinib.

All subjects ≥ 40 kg will receive tofacitinib 5 mg BID oral tablets; however, subjects who cannot swallow oral tablets and all subjects <40 kg will receive a weight-based dose of tofacitinib oral solution (1 mg/mL) BID with a maximum dose of tofacitinib 5 mg BID. The 5 mg BID dose of tofacitinib will be evaluated in a staggered fashion (cohorts of 7 subjects followed by safety review, as described under “Dose Selection” in [Section 3.4](#).

Clinical assessments, including laboratory testing, will be performed at Baseline (Day 1) prior to the start of tofacitinib treatment, on Day 3, Day 7, Day 14, Week 4, and thereafter on a monthly basis.

If subjects are using CS treatment at study start, doses must be stable and ≤ 1.0 mg/kg/day up to 30 mg/day oral prednisone (or equivalent), in the last week before the first study drug dose (Day 1) and remain stable for the full duration of the Open-label Phase Part 1. Subjects who are not taking CS or are not required to taper CS dosing (subjects taking doses of corticosteroids ≤ 0.2 mg/kg/day) must be able to maintain an Adapted JIA ACR 30 response for at least 4 weeks in the Open-label Phase Part 1 will be allowed to proceed to Part 2 of the Open-label Phase. CS doses >0.2 mg/kg/day must be tapered in Part 2 of the study. Before CS tapering can start in the Open-label Phase Part 2, subjects will be required to achieve an Adapted ACR 50 response in the Open-label Phase Part 1 in addition to maintaining an Adapted ACR 30 response for 4 weeks. The duration of the Open-Label Phase Part 1 for each subject is variable but will be no longer than 16 weeks.

Adapted JIA ACR 30 Response/Adapted JIA ACR 50 Response are defined as absence of fever due to sJIA (temperature $\leq 38^\circ$ C/ 100.4° F) in the preceding 7 days along with an improvement of at least 30% / 50% from baseline (Day 1 of study drug before first tofacitinib administration) in at least 3 of the 6 JIA core components, with worsening of $\geq 30\%$ / $\geq 50\%$ in no more than 1 of the remaining components, which include:

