5.5. Administration

During the open-label phase (12 to 40 weeks), all subjects will receive active tofacitinib oral tablets or oral solution twice daily (BID) orally, approximately 12 hours (\pm 2 hours) apart, in the morning and evening, at a dosage based on the subject's body weight as specified in Table 3. In the open-label phase, subjects \geq 40 kg will receive tofacitinib 5 mg BID as oral

tablets or solution (1 mg/mL). Subjects who are unable to swallow tablets will have the option of taking oral solution. All subjects <40 kg will receive an equivalent weight-based lower dose of tofacitinib oral solution (1 mg/mL) BID as specified in Table 3. At each visit the appropriate dose will be assigned via the IRT system based on the subject's weight.

Subjects should swallow investigational product tablets whole and not manipulate or chew them prior to swallowing. Dosing cards with clear written instructions on how to properly take study medication will be provided to the subject with study medication.

Table 3. Study Treatment Dosing and Administration

Body Weight (kg)	Dosage Regimen (Run-In Phase: Tofacitinib, Double-Blind Phase: Tofacitinib/Placebo)
	5 mg BID dose level
5 - <7	2 mg (2 mL oral solution) BID
7 - <10	2.5 mg (2.5 mL oral solution) BID
10 - <15	3 mg (3 mL oral solution) BID
15 - <25	3.5 mg (3.5 mL oral solution) BID
25 - <40	4 mg (4 mL oral solution) BID
≥40	5 mg (one 5 mg tablet or 5 mL oral solution) BID

After the 12-40 weeks open-label phase, eligible subjects will proceed to the double-blind, placebo-controlled phase. They will be randomized in a 1:1 ratio to receive either active tofacitinib oral tablets/oral solution or matching placebo oral tablets/oral solution, twice daily (BID), approximately 12 hours (±2 hours) apart, in the morning and evening, at a dosage based on the subject's body weight as specified in Table 3.

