**Table 4. Summary of Efficacy Analyses**

Endpoint	Estimand and Analysis Type	Population	Data Inclusion and Rules for Handling Intercurrent Events and Missing Data	Analysis Model
	Supplementary estimand  Estimand 5 Treatment Policy Strategy  Supplementary analysis	DBFAS	All data collected including those through Week 52 post randomization from study A3921165 and flare data from study A3921145 and will be included regardless of intercurrent events.  Missing data are not imputed, assuming censoring at random.	Unstratified log-rank test, KM  Cox Proportional Hazard Ratio
	Supplementary estimand  Estimand 5 Treatment Policy Strategy  Sensitivity analysis	DBFAS	All data collected including those through Week 52 post randomization from study A3921165 and flare data from study A3921145 and will be included regardless of intercurrent events.  Missing data will be imputed, assuming censoring not at random.	Tipping point analysis, unstratified log-rank test
Time to disease flare in DB phase by subgroups: age, body weight, geographic region, formulation, OL baseline oral corticosteroids use, DB baseline oral corticosteroid use, OL baseline MTX use, prior bDMARD experience	Primary estimand  Estimand 1 Composite Strategy  Subset analysis	DBFAS	Investigational product discontinuation due to study end and end of study treatment after clinical remission are treated as non-flare and censored. Investigational product discontinuation for any other reason are treated as disease flare.  Missing data are not imputed, assuming censoring at random.	KM, Cox Proportional Hazard Ratio
Occurrence of disease flares by DB visit	Primary estimand  Estimand 1 Composite Strategy	DBFAS	Investigational product discontinuation due to study end and end of study treatment after clinical remission are treated as non-flare and censored. Investigational product	KM

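### The formulation subgroup excludes anyone who takes both tablet and solution, with no time anchor, so membership depends partly on staying flare-free; the effect is small and one line of SAP text removes it

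*SAP*

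**What the plan says.** SAP 6.4 sets out the age-group analyses and then states: "Subgroup analyses similar to the above age group analyses (Estimand 1 and Estimand 2) will also be presented for" a list of further factors. One is formulation, tablet or solution, with the rule "Note: subjects who take both formulations will be excluded". SAP Table 4 carries it forward ("Time to disease flare in DB phase by subgroups: age, body weight, geographic region, formulation") and has a matching row for ACR 30/50/70 response and inactive disease. Neither place says whether the open-label phase, the double-blind phase or both count towards taking both forms. The other patient-level factors are fixed in advance: age at enrollment, baseline weight, steroid use at open-label Day 1 and at randomization, methotrexate use at open-label Day 1, and biologic experience up to that day.

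Formulation follows weight. Protocol 3.2.1 says that "subjects who cannot swallow oral tablets and all subjects <40 kg will receive a weight-based dose of tofacitinib oral solution". From 40 kg, Protocol Table 3 gives "5 mg (one 5 mg tablet or 5 mL oral solution) BID", and Protocol 5.5 adds: "Subjects who are unable to swallow tablets will have the option of taking oral solution". Protocol 5.5 also states: "At each visit the appropriate dose will be assigned via the IRT system based on the subject's weight". That sentence stands in the paragraph on the open-label phase, but Table 3 is headed for both phases, and the double-blind paragraph of 5.5 again ties dosage to weight through Table 3. Protocol 5.4.1 supplies both forms, blinded, for the double-blind phase. Protocol 3.3 and 6.8 end a subject's participation at flare.

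**The concern.** A child who starts the double-blind phase on solution and flares early never has the chance to change form, so that child stays in the solution subgroup as an event. The same child, if still flare-free on passing 40 kg and moved to tablets, is deleted together with all the flare-free time already accrued. Membership is therefore settled partly by the outcome being summarized.

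For time to flare (Estimand 1), the deletion makes both arms look worse. If the drug works, more tofacitinib children last long enough to switch, so more are deleted from that arm and the subgroup hazard ratio moves towards 1.

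For by-visit responses (Estimand 2), SAP 2.3.2.1 keeps a child who stops treatment because of flare as a non-responder through Week 52. A responder who changes form late is deleted from every visit, including those before the change.

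What is at stake is a fair reading of how the solution performs against placebo.

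**Working it through.** **The plan's figures.** The documents give no number for this exclusion. The inputs are those of SAP 5.1: placebo median 236 days, HR 0.36, 1:1 allocation. A two-look log-rank calculation with these inputs, 28 and 37 flares and the stated spending functions reproduces SAP Table 2: z = −1.973 and −2.586, futility z = −1.240, power 80.4%.

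**Who is still flare-free and so can switch.** With exponential times, S(t) = exp(−λt), where λ = ln 2/236 = 0.002937 per day on placebo and 0.36λ on tofacitinib.

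| Time | Placebo | Tofacitinib |
|---|---|---|
| Week 24 (168 d) | 61.1% | 83.7% |
| Week 52 (364 d) | 34.3% | 68.1% |
| Week 104 (728 d) | 11.8% | 46.3% |

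Illustration at the boundary: a child of 38 kg gaining an assumed 3 kg/year reaches 40 kg at 2/3 × 365 = 243 days. By then 48.9% of such children on placebo and 77.3% on tofacitinib are flare-free, and only they can be deleted.

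**Effect on the solution subgroup.** I simulated 400,000 solution starters per setting, with visits every 28 days, and deleted a child who reached 40 kg at a visit before flare or censoring and changed to tablet. The Cox HR was then taken in those kept. Weight (uniform up to 40 kg), growth, follow-up and the share switching are assumptions; none is in the documents. All switch unless stated.

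| Starting weight, gain, follow-up | Deleted, placebo | Deleted, tofacitinib | HR in those kept |
|---|---|---|---|
| 10–40 kg, 3 kg/y, 52 wk; half switch, half leave at Week 24 in remission | 2.2% | 2.8% | 0.363 |
| 10–40 kg, 3 kg/y, 52 wk | 5.6% | 7.7% | 0.363 |
| 10–40 kg, 5 kg/y, 52 wk | 9.3% | 12.7% | 0.365 |
| 25–40 kg, 5 kg/y, 52 wk | 18.7% | 25.3% | 0.375 |
| 10–40 kg, 5 kg/y, 104 wk | 12.9% | 22.3% | 0.385 |
| 25–40 kg, 5 kg/y, 104 wk; half leave at Week 24 in remission | 17.9% | 28.2% | 0.409 |
| 25–40 kg, 5 kg/y, 104 wk; half switch | 13.1% | 22.2% | 0.381 |
| 25–40 kg, 5 kg/y, 104 wk | 26.0% | 44.6% | 0.439 |

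With censoring uniform over 90–900 days and growth of 2.5–4 kg/year, starters of 12–40 kg give about 0.37 and starters of 30–40 kg give 0.39 to 0.43.

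Both arms look worse. In the 10–40 kg, 3 kg/year, 52-week row, the flare-free share at the end falls from 68.0% to 66.9% on tofacitinib and from 34.3% to 32.9% on placebo. The deleted children were flare-free at the change of form, but 24% to 47% of them flare later in these runs.

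**If the drug does nothing.** With a true HR of 1, deletion is equal by arm (for example 18.6% and 18.7%) and the HR stays at about 1.00.

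**Against sampling error.** Protocol 10.1.1 expects 54 randomized. If all 54 started on solution, 27 per arm, the 10–40 kg, 3 kg/year, 52-week row deletes 27 × 0.077 = 2.1 tofacitinib and 27 × 0.056 = 1.5 placebo children. If about 18 of the 37 flares fell among solution takers (an assumption), SE(log HR) ≈ 2/√18 = 0.47, and the 95% interval around 0.36 is 0.36 × exp(±1.96 × 0.47), about 0.14 to 0.91. A shift to 0.37 is ln(0.37/0.36) = 0.03 on the log scale. A shift to 0.44 is 0.20, under half a standard error.

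**Estimand 2.** No size was computed; the direction follows from the deletion rule.

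**The case against.** The best defence is that this hardly matters. It concerns descriptive subgroup summaries in which, by SAP 6.4, hazard ratios may or may not be shown. For the subgroup as planned, all solution takers, the shift is about 0.01 or less over 52 weeks. The larger values need children close to the weight limit or two years of follow-up, and leaving in remission after 24 weeks of inactive disease shortens the time available to switch. All of that stands.

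Three stronger readings are tempting, and the documents do not support them.

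- **Every child who passes 40 kg changes to tablets.** Protocol 3.2.1 makes tablets the usual form from 40 kg, but 5.1.1, 5.5 and Table 3 allow solution there too.
- **The rule always costs the tofacitinib arm more.** That holds only if the drug works. Any deletions for changes before randomization cannot differ by arm beyond chance.
- **This is the trial's only view of solution against tablet.** The subgroup compares tofacitinib with placebo within each form. The baseline weight split at 40 kg, in the same list, gives nearly the same contrast, is fixed in advance and excludes nobody.

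There is also a tension about dosing. Protocol 3.3 has randomized subjects continue the dose they had in the open-label phase, while 5.5 assigns dose by weight. These passages must be reconciled. How they are read affects how many double-blind changes of form occur, and so the size of the effect.

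What the defence does not answer is the structure: nothing in either document gives the rule a time anchor or stops deletion on information that arises after randomization.

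**Conclusion.** The flaw is real and its effect small. As written, the rule lets post-randomization experience decide who is in the formulation subgroup, and in the double-blind phase only children not yet flared can be removed for switching. If tofacitinib works, the solution-subgroup HR is pulled towards 1: from 0.36 to about 0.36–0.37 for all solution starters, and to about 0.39–0.44 only near 40 kg or with long follow-up. These sizes rest on the design HR and median, exponential times, and assumed weights, growth and switching. By-visit responses are affected as well.

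The rule cannot manufacture a benefit for tofacitinib, and it does not touch the primary log-rank test, its boundaries or the full analysis set. A reader should not infer that it would make an effective solution look ineffective; the shift lies well inside the subgroup's sampling error. The case for changing it is that the repair is cheap and also settles which period counts.

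**What to change.** Replace the note in SAP 6.4 with: *Formulation subgroup is defined by the formulation dispensed at the Randomization visit (DB Day 1); no subject is excluded for a later change of formulation.* Apply it to the Estimand 1 and Estimand 2 formulation subgroups in 6.4 and in Table 4, and footnote the number who later switched, by arm.

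The cost is one line of text. SAP 6.5 already lists formulation with start and stop dosing dates for each phase, so no new data are needed. Nobody is then removed for a later change, and in the simulations the subgroup HR stays at the true 0.36. The downside is that a child who switches later contributes some time on the other form to the starting subgroup. That is a smaller problem than selecting on being flare-free, and the footnote makes it visible.

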## 6.5. Baseline and Other Summaries and Analyses

Open-label baseline demographic characteristics will be summarized by age group at enrollment.

### Subject Disposition

Subject disposition will be summarized for both Part 1 and Part 2 of the open-label phase (based on the OLPT1 and OLPT2 analysis sets), including how many subjects entered and completed each part, discontinued investigational product and withdrew from study in each part. The reasons for both investigational product discontinuation and study withdraw from Part 1 and Part 2, and from the double-blind phase will be summarized. In addition, the number of subjects being randomized directly after completion of Part 1 and those randomized after completing Part 2 will be provided. The number of subjects entering, not entering and reasons for not entering A3921145 study from open-label or double-blind phase will also be presented.

The Part 1 and 2 open-label disposition tables will be for all tofacitinib treated subjects. Number of subjects who increased from 5 mg BID to 10 mg BID on Day 14 per previous protocol (original protocol and Protocol Amendment 1) will be footnoted.

For the double-blind phase the number of subjects randomized to each treatment group: tofacitinib 5 mg BID, placebo will be summarized and the reasons for discontinuation from investigational product in DB phase will be displayed based on the DBFAS.

### Drug Exposure

For each phase (OL and DB) the subject's weight, prescribed daily dose, actual daily dose, route, formulation (tablet or solution) along with the start and stop dosing dates and reasons for missed doses will be displayed in listings. The start date of Part 1, Part 2 will be included in the listings to distinguish the doses taken in each OL phase. For subjects receiving oral solution prescribed daily dose will be determined based on the subject's assigned nominal dose and the subject's weight (Table 3).

**Table 3. Investigational Product Dosing and Administration**

Body Weight (kg)	Dosage Regimen (Run-In Phase: Tofacitinib, Double-Blind Phase: Tofacitinib/Placebo)
	5 mg BID nominal dose
5-<7	2 mg (2 mL oral solution) BID
7-<10	2.5 mg (2.5 mL oral solution) BID
10-<15	3 mg (3 mL oral solution) BID
15-<25	3.5 mg (3.5 mL oral solution) BID

**Table 3. Investigational Product Dosing and Administration**

25-<40	4 mg (4 mL oral solution) BID
≥40	5 mg (one 5 mg tablet or 5 mL oral solution) BID

Descriptive statistics for duration of treatment will be provided for Part 1 of the OL (based on OLPT1), Part 2 of the OL (based on OLPT2), and the DB (based on DBSAS).

Additionally, the number and percentage of subjects falling into categories of treatment duration will be summarized. For Part 1 of the OL, the categories will be ≤4 weeks, >4 weeks-≤8 weeks, >8 weeks-≤12 weeks, >12 weeks-≤16 weeks. For Part 2 of the OL 4-week categories will be similar and going up to a maximum of 24 weeks. For the DB 4-week categories will be used as well, with the maximum interval determined by the duration of the study.

## 6.6. Safety Summaries and Analyses

Safety analyses will be carried out using the safety analysis sets for the open-label Part 1, Part 2, and double-blind phase (OLPT1, OLPT2, DBSAS).

All the safety data, including the following, will be summarized descriptively through appropriate data tabulations, descriptive statistics, and graphical presentations:

- Safety laboratory tests will be summarized according to Pfizer standards. Changes from baseline in lab and vital sign values of randomized subjects will utilize both the open-label baseline and the double-blind baseline.
- All the following safety endpoints will be summarized using non-standard tables: serious infections (based on AE database with SOC=“Infections and Infestations” and marked as serious), herpes zoster (including both AE database and adjudicated data), adjudicated opportunistic infections, cytopenias, adjudicated malignancies, adjudicated gastrointestinal (GI) perforations, adjudicated cardiovascular events, adjudicated MAS, clinically significant abnormal laboratory parameters (absolute neutrophil, absolute lymphocyte, serum creatinine, liver tests, lipid levels, and hemoglobin), and validated assessments of growth (body weight and height, refer to [Appendix 3.10](#) for details) and pubertal development (Tanner Stage of Development).
- Subjects meeting discontinuation and monitoring criteria will be summarized.

### 6.6.1. Adverse Events

Adverse events will be summarized according to Pfizer standards. AE's will be summarized by the separate phases: Part 1, Part 2 of the open-label, and double-blind.

An adverse event will be considered a treatment-emergent AE (TEAE) if the event starts during the treatment phase of interest. In all these analyses, all AEs (ie, an infinite lag) will be counted within each study phase, with the reception of the incidence rate (IR) calculation

for events of interest, where the risk period will be up to 28 days within the last investigational product dose, as defined below.

Selected AEs in double-blind phase will be analyzed using incidence rate (IR) and 95% CI and hazard ratio (HR) and 95% CI using a Cox model, including any TEAE, SAE, adjudicated MAS, serious infections (SI) including tuberculosis, varicella and herpes zoster (HZ) and adjudicated opportunistic infections (OI), adjudicated malignancies, adjudicated GI perforations, and adjudicated CV events.

The IR (expressed in unique number of subjects with events per 100 subject-years) for double-blind phase will be defined as the number of subjects with at least one event during the risk period divided by the sum of the durations of exposures for the subjects during the risk period.

The risk period (RP) for the double-blind phase for each subject will span from day of randomization to the earliest of last contact date and last investigational product dose date + 28 days. The last contact date will be the maximum of: AE start date, AE stop date, last study visit date, withdrawal from study date and telephone contact date. If a subject dies, last contact date will be the death date. First events will be counted within the risk period. If a subject did not have an event or had an event but outside the risk period, the subject will be censored at the end of risk period.

$$\text{IR for DB} = (\text{\#of subjects with first events during the DB risk period}) / (\text{sum of durations of subject exposure during the risk period})$$

The numerator of the IR will include subjects counted only once as soon as they experience a first event during their individual risk period defined above.

The denominator will be the sum of the times to event for those who experience an event during the risk period and the lengths of risk periods for those who do not experience an event. If a subject experiences multiple instances of the same event, the time to first occurrence of the event will be considered.

The calculated rate is then multiplied by 100 to yield an IR in units of the number of subjects with events per 100 subject-years. Exact 95% Poisson CI will be provided for IRs as follows.

The 95% CI (corresponding to  $\alpha=0.05$ ) for this IR will be calculated based on the assumption that the actual count of cases (ie, unique subjects with events) arises from an exact Poisson distribution. The approach used in [Daly \(1992\)](#) describing the calculation of exact confidence limits will be used. If  $x$  denotes the actual number of subjects with events, the  $(1 - \alpha) \times 100\%$  confidence limit,  $x_L$  the lower confidence limit and  $x_U$  the upper confidence limit, then the following formula yields values for  $x_L$  and  $x_U$ ,

When  $x > 0$ ,

$$x_L = 0.5 * \chi^2(\alpha/2; 2x) \text{ and } x_U = 0.5 * \chi^2(1 - \alpha/2; 2x+2),$$

When  $x = 0$ ,

$$x_L = 0 \text{ and } x_U = 0.5 * \chi^2(1 - \alpha/2; 2x+2).$$

In the above notation,  $\chi^2(p; n)$  represents the  $p^{\text{th}}$  quantile of the chi-square distribution with  $n$  degrees of freedom. Once  $x_L$  and  $x_U$  are obtained, they are to be adjusted for the at-risk population per 100 subject-years by multiplying by 100.

In addition, the number and percentage of subjects with MAS including both the adjudicated events and per protocol lab criteria will be obtained for Part 1, Part 2 of OL, and DB. The later will be programmatically derived using the following algorithm from protocol Section 7.2.3:

Per protocol, a subject is classified as having MAS if the subject has:

- Fever at a visit plus Ferritin  $>684 \text{ ng/mL}$

AND at least 2 of the following 4 laboratory variables:

- Platelets  $\leq 181 \times 10^9 / \text{L}$ .
- AST  $> 48 \text{ U/L}$ .
- Triglycerides  $> 156 \text{ mg/dL}$ .
- Fibrinogen  $\leq 360 \text{ mg/dL}$ .

A supporting listing with the subjects above mentioned lab values and fever will be provided for the subjects meeting MAS criteria per protocol. Subjects with adjudicated MAS will also be listed.

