6.7.1. Discontinuation from Investigational Product during Randomized Withdrawal Phase

Subjects who discontinue Investigational Product in the double-blind phase, for reasons other than sJIA flare, and who do not rollover to A3921145 LTE study, should continue with the regular scheduled visits every 4 weeks up to and including Week 52. All required procedures and assessments listed above should be performed with the exception of IP dispensing and compliance. Subjects should receive standard-of-care treatment as per local guidelines. There are no protocol restrictions on the use of DMARDs and other disallowed agents, detailed in Appendix 1, for subjects receiving standard of care treatment.

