### Appendix 3.13. Definition and Use of Visit Windows in Reporting

Visit windows will be used for efficacy variables, and for any safety displays that display by scheduled visits.

For an endpoint that consists of multiple components, e.g., Adapted JIA ACR30 and JADAS-27 CRP, the components should be collapsed first in the same visit window to derive the endpoint.

If two or more observations fall into the same visit window, the observation closest to the target day will be used in the analyses. If there is a tie, the later observation will be used.

For efficacy data, the visit windows will be applied to both on-treatment and on-study (both on- and off-treatment) data separately. Note: Data collected in visits on or before the last dosing day +2 days are considered on treatment data. Data collected in visits after investigational product discontinuation day + 2 days are considered off-treatment data. For safety data, only the on-study data visit window will be defined and used, except IR calculations for select adverse events.

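### Double-blind AE count tables and by-visit safety displays pool off-product data with on-product data under the arm, with no on-treatment counterpart

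*SAP*

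**What the plan says.** **Adverse events.** SAP 6.6.1 defines treatment emergence by phase alone: "An adverse event will be considered a treatment-emergent AE (TEAE) if the event starts during the treatment phase of interest". It then states that "all AEs (ie, an infinite lag) will be counted within each study phase". The sentence goes on to exempt the incidence-rate calculation for events of interest (the printed word reception is evidently a slip for exception). That calculation has its own risk period, from "day of randomization to the earliest of last contact date and last investigational product dose date + 28 days". It covers any TEAE, SAEs, adjudicated MAS, serious and opportunistic infections, malignancies, GI perforations and cardiovascular events, with Cox hazard ratios alongside.

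**By-visit safety displays.** SAP Appendix 3.13 applies the efficacy windows to on-treatment data and to "on-study (both on- and off-treatment) data separately". For safety it provides one version: "For safety data, only the on-study data visit window will be defined and used, except IR calculations for select adverse events".

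**Who stays in the study off product.** Under Protocol 6.7.1, children who stop double-blind product for a reason other than flare, and who do not roll over to A3921145, "should continue with the regular scheduled visits every 4 weeks up to and including Week 52". Protocol 3.3 and Schedule of Activities footnote 25 add that this ends earlier if the study concludes. Footnote 25 keeps every visit activity except product dispensing, dosing and compliance, so laboratory tests and AE assessment continue. On treatment during this time, Protocol 6.7.1 says: "There are no protocol restrictions on the use of DMARDs and other disallowed agents". Protocol 9.2 collects AEs to study completion or withdrawal where that is later than 28 days after the last dose.

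**Attribution.** The double-blind safety set (SAP 4.1.2) reports each child under the treatment received. It has no off-product category.

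**The concern.** Taken together, these rules mean that an event starting months after the last dose, in a child who may by then be taking another DMARD, is tabulated as a treatment-emergent event of the tofacitinib or placebo arm. A laboratory value from such a visit enters the arm's by-visit summary in the same way.

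The children concerned are not a random subset. Protocol 8.3.2 and Appendix 7 stop product for serious infection, cytopenia, and transaminase or creatinine criteria, and SAP 6.6 tabulates those same outcomes. Pooling can therefore mislead in either direction: recovery off product dilutes a laboratory signal, while events on a replacement drug add to whichever arm the child came from. SAP 6.6 also summarises children who meet monitoring and discontinuation criteria and states no last-dose limit for that summary, so a child could be counted as meeting a product-stopping criterion after product had already stopped.

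Any TEAE and SAE will appear twice, as a percentage with no lag limit and as a rate cut at 28 days. The numerators need not agree, and nothing in the tables would show the reader why.

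**Working it through.** The plan gives no figure for off-product safety data, so there is none to reproduce. The check is a comparison of the rules, followed by arithmetic that bounds the effect.

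**Rules side by side**

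| Output, double-blind phase | Window | Off-product data included? |
|---|---|---|
| Efficacy by visit (SAP App. 3.13) | On-treatment (last dose + 2 days) and on-study, separately | Separable |
| Incidence rates, and the hazard ratios described with them (SAP 6.6.1) | To last dose + 28 days | Not beyond 28 days |
| AE/SAE counts and percentages (SAP 6.6.1) | Whole phase, infinite lag | Yes, pooled |
| Safety displays by visit (SAP App. 3.13) | On-study only | Yes, pooled |
| Laboratory summaries not by visit (SAP 6.6) | Sponsor standards, not in the documents | Not stated |

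**Inputs.** 54 children randomised 1:1 (Protocol 10.1.1), so 54/2 = 27 per arm. Follow-up to Week 52 (Protocol 6.7.1). Window of last dose + 28 days, or 4 weeks (SAP 6.6.1).

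**Effect of one child.** If a child's first event in a category falls only after the window, the arm's percentage moves by 1/27 = 3.7 points. A child already counted for that category while on product moves nothing.

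**Share of follow-up beyond the window.** For a stop at week w, the share is (52 − (w + 4))/52:

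- Week 8: (52 − 12)/52 = 40/52 = 77% (280 days)
- Week 24: (52 − 28)/52 = 24/52 = 46% (168 days)
- Week 48: (52 − 52)/52 = 0% (0 days)

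**Illustrative range.** The documents give neither the number of such children nor an off-product event rate, so both are assumed: k = 1 to 6 children per arm with no earlier event in the category, stopping at Week 8 to 24, followed to Week 52, with r = 0.2 to 1.0 first events per year. Expected shift = k × (1 − exp(−r × t))/27, where t is the time beyond the window in years.

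- Low end (k = 1, Week 24, r = 0.2): t = 168/365.25 = 0.460; 1 − exp(−0.092) = 0.088; 0.088/27 = 0.3 points.
- High end (k = 6, Week 8, r = 1.0): t = 280/365.25 = 0.767; 1 − exp(−0.767) = 0.535; 6 × 0.535/27 = 11.9 points.

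The range shows what small arms can do. It is not a forecast.

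**The case against.** The strongest reply is that the SAP already supplies an on-treatment result where it matters most. The incidence rates and hazard ratios cover any TEAE, SAEs and the events of special interest, and they stop at 28 days. That stands. A reader might infer that the whole double-blind safety analysis is contaminated; the documents do not support this. A reader might also infer that every laboratory table is affected. The infinite lag is written for AEs only, Appendix 3.13 governs displays by scheduled visit, and the window for other laboratory summaries is simply not stated.

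Second, the affected group may be small. Children who flare or reach clinical remission complete the study (Protocol 3.3), and others may enter A3921145 if eligible. Confirmed pregnancy, and varicella or zoster unless ruled out, lead out of the study (Protocol 8.2.10 and 8.2.6). Follow-up to Week 52 off product came with Amendment 7 in August 2022 (Protocol Appendix 11), and 23 children had been randomised by November 2022 (Protocol 10.1.1). All of this stands, and it is why the total effect cannot be sized.

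Third, counting AEs over the whole study is legitimate. Protocol 9.2 collects them deliberately, causality is assessed for each (Protocol 9.10), and dosing stop dates are listed (SAP 6.5). That also stands, and it argues against demoting the on-study tables: late SAEs, MAS and serious infections in a paediatric trial of an immunosuppressant belong in the main output. It does not explain why the count tables and by-visit displays have no on-treatment version, when the SAP already defines the windows needed.

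**Conclusion.** The point holds for two kinds of output: double-blind AE/SAE count and percentage tables, and safety displays by visit. Both pool off-product data, possibly on other DMARDs, with on-product data under the arm, and the late AEs are labelled treatment-emergent. The incidence-rate and hazard-ratio analyses are not affected.

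The size per child is firm at about 3.7 points, given 27 per arm and a first event in the category that falls after last dose + 28 days. The total is unknown because the number of such children and their stopping times are not given. A reader might take the 77% for a Week 8 stop as typical. It is one stopping time; the same formula gives 46% at Week 24 and 0% at Week 48.

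Nor do the documents support saying that pooling favours one arm: the bias can run either way. This is a modest defect of presentation and labelling. It concerns safety output only and leaves the primary efficacy analysis untouched, but it is cheap to remove.

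**What to change.** Keep the on-study tables as planned, and leave late SAEs, MAS and serious infections in the main output. Then amend the SAP as follows:

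- **6.6.1:** add double-blind AE and SAE count and percentage tables restricted to onset up to last double-blind dose + 28 days, the SAP's own incidence-rate risk period. In the on-study tables and listings, flag events that start off product or show them in a separate column. The flag matters inside the 28 days too, since a replacement drug may already have been started.
- **Appendix 3.13:** define an on-treatment window for safety data, using the existing visit definition (last dose + 2 days), and produce on-treatment by-visit laboratory displays with it.
- **6.6:** apply the same on-treatment rule to laboratory abnormality counts, and state the window for laboratory summaries that are not shown by visit.
- **Disposition:** report by arm how many children stayed in A3921165 off product and for how long, so that readers can judge the difference between the two sets.

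The cost is SAP wording and a second set of standard tables. No data are lost, and neither data collection nor trial conduct changes.
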